6.4.3. Other General Data Handling

- **Age:** Age will be computed from July 1 of the year of birth to the date of Informed Consent, as:

$$(\text{Date of Informed Consent} - \text{July 1 of the year of Birth} + 1) / 365.25.$$
- **Missing Data:**

- All analyses and descriptive summaries will be based on the observed data. Unless otherwise specified, missing data will not be imputed or “carried forward.”
- If the causality (relationship to study drug) of an adverse event is missing, then it will be considered as related to study drug.
- **Baseline Measurements:**
 - **Efficacy analysis including QoL:** The last measurement on or prior to the date of randomization will serve as the baseline measurement. In the event such a value is missing, the first assessment completed prior to the first study drug administration will be used as the baseline assessment so long as this assessment was taken within 7 days of randomization.
 - **Safety analysis:** The last non-missing measurement prior to the first study drug administration will be used as the baseline assessment.
 - **Baseline characteristics:** The last measurement on or prior to the date of randomization will serve as the baseline measurement. In the event such a value is missing, the first assessment completed on or prior to the date of first study drug administration will be used as the baseline assessment.
- **Study Day:**
 - For safety analysis: Study day is calculated as:
 - assessment date – first dose date + 1; if the assessment was performed on or after the first dose day.
 - assessment date – first dose date; if the assessment was performed prior to the first dose date
 - For efficacy analysis including QoL: Study day is calculated as:
 - assessment date – randomization date + 1; if the assessment was performed on or after the randomization date.
 - assessment date – randomization date; if the assessment was performed prior to the randomization date.
- **Duration:** Duration (except duration of study treatment) is calculated as:
 - Duration (days): (End Date – Start Date + 1)
 - Duration (weeks): (End Date – Start Date + 1) / 7
 - Duration (months): (End Date – Start Date + 1) / 30.4375
 - (Average number of days in a month = average number of days in a year /12)
 - Duration (years): (End Date – Start Date + 1) / 365.25
 - (Average number of days in a year = 365.25, reflecting the Julian Year of 3 years with 365 days each and 1 leap year of 366 days)

- **Time-to-event:** The efficacy and QoL event or censoring time (days) is calculated as:
Date of event/censoring – Date of randomization + 1
Investigator’s assessments will be used to derive PFS, TTP, and best tumor response.
- **Data Presentation:** Categorical variables will be summarized in frequency tables, with the counts and percentage of patients in each category. Percentages given in the summary tables will be rounded and thus may not always add up to exactly 100 percent. For continuous variables, summary statistics will include N, mean, standard deviation, median, Q1-Q3, and minimum and maximum values (range).

6.5. Data Analysis

6.5.1. Disposition of Patients

The number of patients enrolled (that is, signed informed consent), randomized, treated, and discontinued (that is, discontinued the study treatment for reason(s) such as disease progression, AE, lost to follow-up, or withdrawal of consent) will be presented by site and treatment group. Patients enrolled but not randomized will be summarized by reason for not being randomized.

The number and percentage of patients who were in the ITT population, in the Safety population, and in the PP population will be summarized. Moreover, the number and percentage of patients still receiving treatment at data cut-off date will be summarized by treatment group. Patients having completed their End of Treatment visit will be presented by reason for discontinuation of study treatment. Patients excluded from the PP population will be summarized by reason for exclusion.

Besides summary tables, by-patient listings will also be generated.

6.5.2. Demographic and Baseline Characteristics

The following demographic and baseline characteristics will be summarized based on the ITT population:

- Sex
- Race
- Ethnicity
- Age (years)
- Age group (<65 vs. ≥65 years; <75 vs. ≥75 years)
- Height (cm)
- Weight (kg)

In addition, the stratification factors (per Interactive Web Response System [IWRS] and eCRF) and the discrepancy between 2 data sources will be summarized based on the ITT population:

- Geographical region (Region 1 vs. Region 2 vs. Region 3)
- Macrovascular invasion presence
- ECOG PS

The following disease characteristics and prior therapy information will be summarized based on the ITT population:

- Duration of Disease (defined as time from diagnosis confirmation to randomization; if the day of diagnosis confirmation is unknown it will be replaced by 15MMMYYYY)
- BCLC stage
- Child-Pugh score
- Etiology of liver disease (hepatitis B vs. hepatitis C vs. other)
- Basis of HCC diagnosis
- Tumor differentiation (well differentiated, moderately differentiated, poorly differentiated, unable to determine, not applicable)
- Number of metastatic sites Involved (0, 1, 2, ≥ 3)
- Extrahepatic spread presence
- Duration of prior sorafenib treatment (<5 months vs. ≥ 5 months)
- Reason for discontinuation of sorafenib (PD, toxicity)
- Time from last sorafenib treatment to randomization (<1 month vs. ≥ 1 month)
- Had any prior locoregional therapy (yes vs. no)
- Macrovascular invasion presence (CRF) (yes vs. no)
- Presence of ascites Grade ≥ 2 (yes vs. no)
- Required medical or procedural management for ascites even if Grade ≤ 1 at the time of study entry

Prior anticancer therapy, preexisting medical condition, previous surgery for HCC, prior locoregional therapy, and prior radiotherapy for HCC will all be presented.

6.5.3. Analysis of Efficacy Data

6.5.3.1. General Considerations

The primary statistical analysis will be conducted in the ITT population following the intent-to-treat principle, including eligible and ineligible patients and based on the treatment group to which patients was randomized (irrespective of which treatment was received). Control of the type I error for multiple testing will be maintained by the sequential gatekeeping testing for the primary and secondary efficacy variables (Section 6.5.3.3). Sensitivity and subgroup analyses of the primary and secondary endpoints will be performed.

The stratification categories used for the primary and secondary analyses are:

- geographic region (Region 1 versus Region 2 versus Region 3)
- macrovascular invasion (yes versus no)
- ECOG PS (0 versus 1)

Unless otherwise specified, all stratified analyses of primary and secondary endpoints will be based on the stratification factors per IWRS.

The final analysis will be conducted once approximately 221 deaths have been observed in the ITT population using a 2-sided nominal significance level of 0.05.

6.5.3.2. Primary Efficacy Endpoint - Overall Survival

The primary analysis will compare the observed OS between the 2 treatment groups (ramucirumab plus BSC versus placebo plus BSC).

The primary OS analysis will be conducted in the ITT population. The comparison will use the log-rank test, stratified by the randomization stratification factors.

Hazard ratio (HR) and its two-sided 95% confidence interval (CI) will be estimated using Cox proportional hazards (PH) model stratified by the randomization strata. Additionally, OS curves will be presented using the Kaplan-Meier method by treatment arm, together with a summary of associated statistics (that is, median OS, 6-months and 1-year OS rates including corresponding two-sided 95% CI). The 95% CI for the median survival time will be calculated according to Brookmeyer and Crowley (1982). The 95% CI for the OS rate difference will also be calculated. The total number of events and censored observations will be presented for each treatment group along with reason for censoring (for example, patient still alive at data cut-off date, lost to follow-up, etc.).

The primary analysis will be performed using the stratification variables as captured by the IWRS.

The following sensitivity analyses are planned:

- An analysis of OS based on the PP population
- An analysis of OS in the ITT population with an unstratified log-rank test
- A stratified analysis of OS in the ITT population using the stratification factors as reported in the eCRF
- An analysis of OS in the ITT population with baseline AFP ≥ 400 ng/mL based on central lab result
- An analysis of OS adjusting the treatment effect for significant prognostic factors (see Section 6.5.3.5)

A listing will be prepared presenting relevant information on the OS (including date of randomization, date of death, date last known to be alive, censoring status, and reason for censoring).

6.5.3.3. Secondary Efficacy Endpoints

A gatekeeping approach to selected secondary endpoints will be applied so as to protect the study-wise type I error rate and to enable inferential statements; each hypothesis is inferentially tested only if each of the preceding hypotheses were rejected. The sequential order of the confirmatory testing after OS in the ITT population will be: 1) PFS in the ITT population; 2) time to deterioration in FHSI-8 total score in the ITT population; and 3) time to deterioration in ECOG PS in the ITT population. Secondary endpoints will be analyzed at the same time as OS and at the same level of significance (1-sided 0.025).

6.5.3.3.1. Progression-Free Survival

The censoring rules in [Table 3](#) and [Table 4](#) will be used for the primary and sensitivity analyses for PFS. PFS will be analyzed using a stratified log-rank test, stratified by the same stratification factors used in the analysis of the primary endpoint, OS. The HR will be generated using a stratified Cox regression model. An additional PFS analysis with an unstratified log-rank test will also be performed. The estimation of survival curves for the 2 treatment groups will be generated using the Kaplan-Meier method. The medians as well as the 3-month and 6-month PFS rates will be provided along with their 95% CI. The total number of events (disease progressions, deaths, total) and censored observations will be presented for each treatment group along with reason for censoring. PFS will be analyzed for the ITT population. Additionally, PFS will be analyzed for the PP population.

A listing will be prepared presenting relevant information on the PFS time (including date of randomization, date of last radiological scan, date of last radiological scan with overall response SD, PR, or CR, date of radiological progression, date of symptomatic progression, date of death, censoring status, and reason for censoring). A separate listing will be prepared using the sensitivity censoring rules.

6.5.3.3.2. Time to Deterioration of FHSI-8

The time to deterioration of FHSI-8 total score will be compared between the treatment groups from stratified (primary) and unstratified log-rank tests. Kaplan-Meier graphs by treatment arm will be produced. If deterioration is not observed, then time to deterioration is censored at the date of the last FHSI-8 assessment for that patient. The HR and 95% CIs will be estimated using Cox's PH regression model, sensitivity analysis may include covariates of assigned treatment and baseline total score.

Additional sensitivity analyses may be performed using definition described in [Section 6.4.2.3](#).

6.5.3.3.3. Time to Deterioration of ECOG PS

The ECOG performance status results will be summarized using frequency distributions for each scheduled visit, including also the best and worst postbaseline value.

Time to deterioration will be analyzed for the ITT population using the Kaplan-Meier method, using an stratified (primary) and unstratified log-rank test. Additional sensitivity analyses may be performed using definition described in [Section 6.4.2.4](#).

Event/Censoring for the time to deterioration analysis:

- Event date is the first date observing the required PS value or deterioration
- Censor at time of the last PS value if no event

In order to investigate the relationship between objective progression and deterioration in ECOG PS, an analysis of changes from baseline in ECOG PS by objective progression (yes vs. no) by tumor measurement period will be performed.

6.5.3.3.4. Objective Response Rate and Disease Control Rate (DCR)

The ORR will be calculated as the number of patients who achieve a best response of CR or PR using the investigator response assessments, divided by the total number of patients randomized to that study arm in the ITT population. Patients who do not have a tumor response assessment for any reason are considered as non-responders and are included in the denominator when calculating the response rate. The RECIST 1.1 will be followed in this clinical trial.

Frequencies for Best Overall Response (BOR) will be presented by treatment group, as well as ORR and DCR observed in each treatment group together with 95% CI.

The ORRs and DCR observed in each treatment group will be compared using the exact Cochran-Mantel-Haenszel test adjusting for the stratification variables as captured by IWRS.

A listing will be prepared presenting relevant information on response (including date of randomization, date of radiological scans, target lesion percentage change, response on target-lesions, response on non-target lesions, new lesions, and overall response for each tumor assessment, BOR).

6.5.3.3.5. Time to Radiographic Progression

The censoring rules presented in [Table 5](#) will be used for the analysis for TTP. The treatment groups will be compared using the stratified log-rank test, as well as unstratified log-rank test. The estimation of survival curves for the 2 treatment groups will be generated using the Kaplan-Meier method. Median TTP will be provided with a two-sided 95% CI. CIs will be computed in the same way as for OS. The HR will be generated using the stratified as well as unstratified Cox regression model.

Time to radiographic progression will be analyzed for the ITT population.

6.5.3.4. Subgroup Analysis

Subgroup analyses will be performed for OS, the primary endpoint, and PFS. Only unstratified analysis will be performed on each subgroup. Each analysis will use the similar methodology as for the primary analysis. A Forest plot of the estimated HRs with 95% CIs will be provided for subgroups with sufficient number of events (≥ 15).

The following is the list of subgroups:

- Gender (Males vs. Females)
- Age (< 65 years vs. ≥ 65 years)
- Race (white vs. Asian vs. all others)
- Geographical region (Region 1 vs. Region 2 vs. Region 3)
- Etiology of liver disease (hepatitis B vs. hepatitis C vs. other)
- Presence/absence of extra-hepatic metastases
- Presence/absence of macrovascular invasion
- BCLC score (B vs. C)
- Baseline ECOG PS (0 vs. 1)
- Had any prior locoregional therapy

- Reason for discontinuation of sorafenib (PD vs. toxicity)

Tests within each subgroup and tests for subgroup-by-treatment interaction terms will use an unstratified test and unstratified Cox PH model.

The goal of subgroup analyses is to assess internal consistency of study results and whether there is significant treatment heterogeneity across any of the subgroups. Since, even if all patient 'groups' benefit to exactly same extent, smaller or larger estimated effects, even negative effects, may be seen for some subgroups simply by chance alone. Without appropriate interpretation, this can lead to erroneous conclusion in one or more subgroups, in particular where differential treatment effects are not expected across any of the factors assessed. In order to assist with interpretation of the subgroup results, the methodology of Fleming (1995) may be followed to provide background information on the extent of variability that might be expected by chance alone.

6.5.3.5. Analysis Adjusting for Covariates

As supportive analysis, the primary (OS) and secondary (PFS) efficacy endpoints will also be analyzed after adjusting for selected prognostic factors. Potential prognostic factors include the stratification factors and other factors as listed in the list of subgroup analyses in Section 6.5.3.4.

Hazard ratio for treatment effect will be estimated using an unstratified multivariable Cox PH model to be constructed by selecting variables among all the potential variables using stepwise selection method with entry p-value 0.05 and exit p-value 0.1. The covariate selection process will be based on the entire ITT population. The treatment factor will be kept out of the model throughout the covariate selection process and only added into the final model. HR for treatment effect and corresponding 95% CI will be estimated from the final model.

6.5.3.6. Restricted Mean Difference Analysis

The common method for describing benefit on the time scale is to calculate the difference in median event time between the two treatment arms. An alternative method for describing benefit on the time scale is to estimate the average difference between the Kaplan-Meier (KM) curves. This corresponds to calculating the difference in the average time to event for the 2 treatment arms (Irwin 1949; Karrison 1997; Meier et al. 2004). Similar to the HR, this method uses all of the available information across the KM curves, but has the additional advantage of assessing benefit on the time scale.

To estimate an improvement in OS with ramucirumab, we will follow the method of Irwin (1949) detailed in Karrison (1997) and Meier (2004) for estimating the 'difference in average OS', which we will refer to more formally as the restricted mean difference in OS. The area under each KM curve will be calculated using numerical integration (trapezium rule) per Karrison and implemented in SAS using PROC LIFETEST. The difference between treatment arms and a CI for the difference will be formed.

Since the KM curve may be ill-determined beyond a certain range, or even undefined (if the longest observation is censored), for evaluation and comparison of means, the area under each KM curve will be calculated between time 0 and restriction time T, which is why this is referred

to as a "restricted mean". Following the suggestion of Karrison, the restriction time T will be chosen as largest time point t such that the standard error (SE) of the survival estimate at time t in each treatment group is no more than 0.075. For this purpose, we will use the simple, albeit conservative, formula proposed by Peto et al. (1977) for calculating the SE of S(t) as:

$$SE(S(t)) = S(t)\sqrt{(1 - S(t))/n(t)},$$

where n(t) is the number of patients still at risk at time t.

Besides for OS, similar restricted mean analysis can be constructed for PFS.

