6.2.2. Determination of Sample Size

The primary objective of this study is to compare ramucirumab versus placebo in terms of OS in patients with advanced HCC after intolerance or progression on prior sorafenib. The sample size was determined based on the following assumptions:

- hazard ratio (treatment/control) of 0.67, with median OS of 4.5 months in the placebo arm and 6.7 months in the ramucirumab arm
- the randomization ratio is 2:1 (ramucirumab:placebo)
- the overall significance level will be controlled at 1-sided 0.025 (2-sided 0.05)
- the Type II error rate is 20%; that is, the statistical power of the trial is set to 80%

Under the assumptions above, the final analysis will be performed when at least 221 deaths have been observed. Therefore, the study will randomize approximately 279 patients (that is, 20% censoring rate including dropouts, with approximately 186 patients randomized to the ramucirumab arm and 93 patients randomized to the placebo arm).

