6.5.5.1. FHSI-8 Analyses

The proportion of patients in each arm with deterioration in scores, improvement in scores, and stable scores at specific time points will be presented both in a summary table and graphically using stacked bar charts. The proportion of patients who deteriorated at each assessment time point may be compared using Fisher's exact test. Patients with no data will be considered deteriorated.

FHSI-8 score will be summarized descriptively at each assessment time by treatment arm, as well as changes from pre-treatment visit, provided at least 30% of the patients have an FHSI-8 score at that time point. Best and worst responses across all the visits will also be summarized in a table.

The time to deterioration of FHSI-8 individual item will be compared between the treatment groups from stratified and unstratified log-rank tests. The HR and 95% CIs will be estimated using Cox's PH model, covariates may include assigned treatment and baseline score.

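### The restricted-mean OS difference and the FHSI-8 proportion test leave out the stratification factors, so both are mildly conservative if those factors are prognostic

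*SAP*

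**What the plan says.** Randomisation is stratified by region (three levels), macrovascular invasion and ECOG PS (Protocol 9.3, SAP 6.2). Protocol 8.2 says the factors were chosen because they are expected to relate to outcome, and that stratifying should reduce bias and add power.

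Most of the SAP's comparisons follow the design:

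- OS (SAP 6.5.3.2): "The comparison will use the log-rank test, stratified by the randomization stratification factors". The Cox model for the HR is stratified too.
- PFS and TTP (6.5.3.3.1, 6.5.3.3.5): stratified log-rank test and Cox model.
- Time to deterioration in FHSI-8 and in ECOG PS (6.5.3.3.2, 6.5.3.3.3): the stratified log-rank test is labelled primary.
- ORR and DCR (6.5.3.3.4): "compared using the exact Cochran-Mantel-Haenszel test adjusting for the stratification variables as captured by IWRS".

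Two comparisons do not. In 6.5.3.6 the area under each arm's Kaplan-Meier curve is computed up to T, after which "The difference between treatment arms and a CI for the difference will be formed". In 6.5.5.1, "The proportion of patients who deteriorated at each assessment time point may be compared using Fisher's exact test". Neither passage mentions strata. SAP 6.5.3.1 says that stratified analyses take their factors from the IWRS, but this does not make these two analyses stratified. Where the SAP wants unstratified subgroup analyses (6.5.3.4), it says so.

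**The concern.** Stratified randomisation with prognostic factors reduces the true sampling variance of the difference between arms. A variance formula that ignores the strata still includes the between-stratum variation that the design has balanced. The interval is then too wide and the test undersized.

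SAP 6.5.3.6 presents the restricted mean as its way of expressing survival benefit in units of time, so it will be read beside the stratified HR. The two could give different impressions partly because only one uses the strata. The FHSI-8 proportions would likewise be tested differently from the SAP's other proportions. What is at stake is some precision in two supportive analyses.

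**Working it through.** **Inputs from the documents.** 279 patients, 2:1 allocation, 221 deaths, 2-sided alpha 0.05, 80% power, and "hazard ratio (treatment/control) of 0.67, with median OS of 4.5 months in the placebo arm and 6.7 months in the ramucirumab arm" (SAP 6.2.2). Strata: 3 × 2 × 2 = 12 cells, so the 93 placebo patients average 93/12 ≈ 8 per cell.

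**The plan's own figure.** Schoenfeld's formula gives deaths = (1.960 + 0.842)² / [(2/3)(1/3)(ln 0.67)²] = 7.85 / (0.2222 × 0.1604) ≈ 220.2, rounded up to 221. This matches. Dividing by 0.80 gives 277 patients, against 279 stated.

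**Assumptions.** Blocks of 6 within strata, 24-month accrual, exponential survival, factor prevalences and all prognostic effects. The documents give none of these.

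**Restricted mean.** Two simulations at treatment HR 0.67 compared the unadjusted Kaplan-Meier difference with a covariate-adjusted one (in run B, within-arm pseudo-values regressed on treatment and the main effects of the three factors, with robust variance). Run A fixed T at 12 months (400 trials per scenario). Run B set T by the SAP's rule of SE ≤ 0.075 (3,000 trials per scenario; mean T about 20-22 months). SEs are in months.

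| Run | Assumed factor HRs | Unadjusted SE | Adjusted SE | Ratio |
|---|---|---|---|---|
| A | ECOG 1.3, invasion 1.3 | 0.533 | 0.529 | 1.008 |
| A | 1.5, 1.5 | 0.537 | 0.525 | 1.023 |
| A | 2.0, 1.8 | 0.542 | 0.510 | 1.063 |
| B | none | 0.765 | 0.768 | 0.996 |
| B | invasion 1.4, ECOG 1.4, region 1.2 | 0.789 | 0.775 | 1.018 |
| B | 2, 2, 1.5 | 0.865 | 0.799 | 1.083 |

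A further simulation put the adjusted SE about 1.5% smaller under moderate effects and 6% smaller under strong effects, with no gain if there are none.

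In absolute terms, the half-width in run A's strong scenario falls from 1.96 × 0.542 = 1.06 to 1.96 × 0.510 = 1.00 months, about two days. In run B's strong scenario it falls from 1.96 × 0.865 = 1.70 to 1.96 × 0.799 = 1.57 months, about four days.

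Three checks on the mechanism, all from run B:

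- *The unadjusted SE overstates the sampling SD.* Under the null, mean SE over empirical SD is 0.691/0.690 = 1.00 (no effects), 0.715/0.700 = 1.02 (moderate) and 0.772/0.723 = 1.07 (strong). Type I error is 5.1%, 4.7% and 3.8%. After adjustment it is 5.1%, 5.2% and 5.6%.
- *Stratified randomisation is the cause.* With strong effects but unstratified blocks, the unadjusted ratio is 0.97 instead of 1.07.
- *Adjustment leaves the target unchanged.* A difference in restricted means is collapsible. The mean estimates are 2.227 and 2.228 months (moderate), and 2.180 and 2.182 (strong). The empirical SDs also barely differ (0.776 and 0.775; 0.798 and 0.796): what adjustment corrects is the reported SE.

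**FHSI-8 proportions.** Assumed: 50% placebo deterioration, treatment OR 0.5, 2,000 trials per scenario (Monte Carlo error about 1 point). Power, %:

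| Factor OR | Fisher | Exact CMH | Asymptotic CMH | Exact CMH minus Fisher |
|---|---|---|---|---|
| 1.0 | 74.0 | 74.2 | 76.4 | 0.2 |
| 1.5 | 73.3 | 74.5 | 77.2 | 1.2 |
| 2 | 71.0 | 72.8 | 74.9 | 1.8 |
| 3 | 64.7 | 70.7 | 73.2 | 6.0 |

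A second run of the exact test gave 0-1 points up to OR 1.5, 3 at OR 2 and 6 at OR 3. At 80% placebo deterioration the gains are 0.1, 1.7 and 4.0 points at ORs of 1.5, 2 and 3. A rate that high is plausible, because 6.5.5.1 counts patients with no data as deteriorated. The exact CMH test's own size was 3.8-4.6%.

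**The case against.** The other side has a good deal right.

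- **Nothing decisive depends on either analysis.** Both lie outside the gatekeeping sequence in SAP 6.5.3.3, and the Fisher test is optional. The confirmatory FHSI-8 analysis is time to deterioration, whose primary test is already stratified. The error is in the conservative direction.
- **The restricted mean keeps ordinary company.** Medians, OS rates and the interval for the OS rate difference (6.5.3.2) also name no strata. The SAP plans unstratified log-rank tests and an unstratified multivariable Cox model that can select the stratification factors (6.5.3.5). The mismatch with the primary analysis is therefore not an anomaly in itself.
- **The size depends on assumed effects.** At HRs of 1.3 the restricted-mean gain is under 1%. Under strong effects the adjusted analysis ran at 5.6%, slightly above nominal.
- **The method is a preference.** A statement that both analyses are deliberately unstratified would also end the silence.

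All of this limits the point's weight. It does not remove the point: the factors are available, and the SAP uses them in its other between-arm comparisons of efficacy.

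Two stronger readings are tempting and are not supported. A reader might infer that a restricted-mean test loses power; in run B's strong scenario, rejection rises from 72.6% to 78.0% with adjustment. SAP 6.5.3.6 plans an estimate and interval, not a test, and under moderate effects the figures are 80.4% and 81.5%. A reader might also compare Fisher's test with the asymptotic CMH test and see gains of 2.4 to 8.5 points. SAP 6.5.3.3.4 specifies the exact version, which shares much of Fisher's discreteness. The step from exact to asymptotic accounts for 2.1 to 2.7 points of that apparent gain in every row.

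**Conclusion.** The point holds as a minor, optional improvement. Neither SAP 6.5.3.6 nor the Fisher comparison in 6.5.5.1 uses the randomisation factors, and both are mildly conservative if those factors are prognostic.

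The restricted-mean interval is then about 1-2% wider than needed under moderate effects and about 6% under strong effects, reaching 8% in the most extreme scenario run. Exact CMH in place of Fisher gains about 0-3 points of power for factor ORs up to 2 and about 6 points at 3. With non-prognostic factors neither change gains anything material. All these sizes rest on assumed prognostic effects, prevalences, block size and accrual.

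A reader might infer that the unadjusted analyses are biased or inflate type I error, or that they weaken the OS conclusion. The documents do not support this: the primary analysis is stratified, and alpha and sample size do not depend on either analysis.

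**What to change.** In SAP 6.5.3.6, keep T and the arm-specific areas. Add a difference and 95% CI adjusted for the main effects of region, macrovascular invasion and ECOG PS as recorded in the IWRS, for example by pseudo-value regression with a robust variance. Show it beside the unadjusted Kaplan-Meier difference. Main effects are preferable to 12 separate cells, given about 8 placebo patients per cell.

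In SAP 6.5.5.1, if the deterioration proportions are compared, replace Fisher's test with the stratified exact CMH test already specified in 6.5.3.3.4.

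The cost is a few sentences of SAP text and a few lines of code. No new data are needed.

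### The restricted-mean cut-off (SE at most 0.075) binds too late to protect against an unreliable tail, and the trapezium wording leaves room for a small shift toward ramucirumab

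*SAP*

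**What the plan says.** SAP 6.5.3.6 offers the restricted mean difference as a description of benefit on the time scale, for OS and optionally for PFS. It restricts the mean because the Kaplan-Meier curve may be poorly determined, or undefined, late on. Its rule for the horizon reads "restriction time T will be chosen as largest time point t such that the standard error (SE) of the survival estimate at time t" does not exceed 0.075 for either arm. The SE is the Peto formula, S(t)·√((1 − S(t))/n(t)), which the SAP describes as conservative. The area is to be obtained by "numerical integration (trapezium rule") and implemented in PROC LIFETEST.

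The section sets no minimum number at risk and no fixed horizon. It does not say what happens if the SE crosses the limit more than once, or once S(t) or n(t) reaches zero.

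The design inputs are in SAP 6.2.2: "hazard ratio (treatment/control) of 0.67, with median OS of 4.5 months in the placebo arm and 6.7 months in the ramucirumab arm"; 186 and 93 patients; "the final analysis will be performed when at least 221 deaths have been observed".

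**The concern.** The restriction exists to keep an unreliable tail out of the estimate. A cap on the absolute SE of S(t) may not do that. As S(t) approaches zero the formula returns a small SE however few patients remain, so the rule can accept a horizon held up by one person. The SE is also not monotone in t, so the largest qualifying time can lie beyond an earlier breach. The reported months gained would then refer to a horizon set by one or two late placebo patients and unknown until the data are in.

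The second matter is the integration method. A Kaplan-Meier curve is a step function. Sloping lines between successive event points cut area from both arms, and cut more from the smaller one. Under 2:1 allocation that favours ramucirumab.

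**Working it through.** **Design figures first.** From SAP 6.2.2: HR 0.67, "the randomization ratio is 2:1 (ramucirumab:placebo"), "the overall significance level will be controlled at 1-sided 0.025 (2-sided 0.05") and "the Type II error rate is 20%; that is, the statistical power of the trial is set to 80"%. The Schoenfeld formula gives

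(1.960 + 0.842)² / [(2/3)(1/3)(ln 0.67)²] = 7.849 / (0.2222 × 0.1604) ≈ 220.2, so 221 deaths, as stated.

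With "20% censoring rate including dropouts", 221/0.80 ≈ 277, against 279 planned. The SAP gives no figure for T or for the restricted mean, so there is none to reproduce.

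**SE without censoring.** The formula reduces to √(S(1 − S)/N), largest at S = 0.5:

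- placebo: √(0.25/93) = 0.052
- ramucirumab: √(0.25/186) = 0.037

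Reaching 0.075 would need N below 0.25/0.075² ≈ 44 in an arm.

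**SE with censoring.** The limit is broken only when n(t) < S²(1 − S)/0.075²:

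| S(t) | n at risk below which the limit is broken |
|---|---|
| 0.30 | 11.2 |
| 0.20 | 5.7 |
| 0.15 | 3.4 |
| 0.10 | 1.6 |
| 0.05 | 0.4 (never) |

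**Where T falls.** Simulation of 2,500 trials per row: 186/93 patients, exponential survival with medians 6.7 and 4.5 months, no dropout, data cut at the 221st death, T capped at the end of the shorter curve. The documents give no accrual pattern, so uniform accrual is an assumption. With 29 months the cut falls near month 32, the study length in the protocol synopsis.

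| Accrual (months) | Limit ever exceeded | Median T (months) | T / last placebo time | Exactly 1 placebo patient at risk at T | Exact difference, months (SD) | Trapezium shift (months) |
|---|---|---|---|---|---|---|
| 12 | 66% | 17.7 | 95.9% | 57% | 2.024 (0.725) | +0.052 |
| 18 | 36% | 20.1 | 97.2% | 80% | 2.183 (0.774) | +0.064 |
| 24 | 16% | 22.0 | 98.1% | 90% | 2.305 (0.804) | +0.077 |
| 29 | 8% | 23.5 | 98.7% | 95% | 2.392 (0.836) | +0.083 |

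At most 3 placebo patients were at risk at T in at least 97% of trials in every row. A repeat of the simulation, measured against the shorter arm's follow-up, put T at 97 to 99.6% of it, with a median of 1 placebo patient at risk. Taking the first crossing instead of the largest qualifying time moves median T by 0.1 month at most, so the non-monotone SE is a gap in the wording more than a driver of the result.

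At a fixed T of 12 months (29-month accrual) the exact difference is 1.38 months (SD 0.53), with about 10 placebo patients at risk.

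**Trapezium shift.** Joining event points loses half of (drop × interval) at each step. With drops of about 1/N this sums to about T/(2N) per arm:

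- placebo loses T/186 and ramucirumab loses T/372
- the difference moves by T/186 − T/372 = T/372, which is 0.048 month at T = 18 and 0.065 at T = 24

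Simulated shifts are slightly larger: +0.05 to +0.08 above, and +0.06 to +0.09 in the repeat. With equal medians of 4.5 months the shift remains (+0.066 and +0.083 at 18- and 29-month accrual). With arms of 140 and 139 it vanishes (−0.002 and 0.000). Allocation, not efficacy, causes it. At 29-month accrual it is 0.083/0.836 ≈ 0.10 of the SD.

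**The case against.** - **The T rule is an explicit, prespecified algorithm with a cited basis.** It leaves little analyst discretion and serves the SAP's aim of using the whole curve. This stands: choosing 12 months instead is partly a choice of estimand, which is why the fixed horizon should be added and not substituted.
- **How often the limit is reached depends on assumptions.** It was exceeded in 8% to 66% of trials by accrual, and in 38% to 79% with longer assumed survival (8.5 and 7.0 months). This also stands, so it would be wrong to say the rule never operates. When it does, it removes only the last few percent of follow-up: with longer survival T was still 94 to 96% of the last placebo time, with a median of 1 or 2 at risk.
- **The trapezium shift may not occur.** The same sentence names PROC LIFETEST. If that procedure's own step area is used, or if the vertical drops are included as vertices, there is no shift. The wording is ambiguous, not demonstrably wrong.

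A reader might infer that the T rule itself inflates the benefit. It does not: with equal medians and exact step area the mean difference was −0.034 and −0.032 month (18- and 29-month accrual). A reader might also infer that the later T wastes precision. The absolute SD is larger, but estimate over SD is 2.392/0.836 ≈ 2.86 at the rule's T, against 1.38/0.53 ≈ 2.60 at 12 months.

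**Conclusion.** The SE limit does not do the job SAP 6.5.3.6 gives it. Under exponential survival at the design medians and assumed accrual of 12 to 29 months, it leaves T almost at the end of the shorter arm's follow-up, typically with one placebo patient at risk. This is the more material half of the point. The trapezium wording is a minor correction: about 0.05 to 0.09 month toward ramucirumab, around a tenth of an SE, and only if trapezia join event points.

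The gap between 2.39 months at the rule's T and 1.38 at 12 months should not be read as bias; these are different estimands. Nothing here affects the conclusion of the trial: OS is tested by the stratified log-rank test (SAP 6.5.3.2), and the restricted mean is outside the gatekeeping sequence (SAP 6.5.3.3). SAP 6.5.3.2 also already reports 6-month and 1-year OS rates. The consequence is confined to how a descriptive benefit in months is read.

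**What to change.** In SAP 6.5.3.6, before unblinding:

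1. Delete the reference to the trapezium rule and state that the area under the Kaplan-Meier step function is computed exactly up to T in PROC LIFETEST.
2. Keep the data-driven T, and add a restricted mean difference at a fixed T, for example 12 months, which matches the 1-year OS rate already planned. Report the number at risk in each arm at both horizons.
3. State how T is set if the SE crosses 0.075 more than once, or if S(t) or n(t) reaches zero.

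The cost is a few sentences and one extra descriptive estimate. The fixed-horizon figure in months will be smaller, and the text should say that this reflects the shorter horizon. The protocol's statistical sections do not describe a restricted mean, and Protocol 12.2.1 allows clarifications of this kind in the SAP before the aggregate database is unblinded.
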